7 CONCURRENT MEDICATIONS

All participants should be maintained on the same medications throughout the entire study period, as medically feasible, with no introduction of new chronic therapies.

7.1 Allowed Medications and Treatments

Standard therapy for epilepsy and related conditions is allowed except for treatments noted in the exclusion criteria described above and as noted in the prohibited medications section below. A stable therapeutic regimen between screening and Visit 1 is the goal, as well as through the baseline period. Once enrolled and started into the baseline observation period, changes in AED medication regimen are not permitted unless it is solely for dose adjustments secondary to sub- or super-therapeutic serum levels. Participants that have been on a chronic AED regimen will be mandated to continue them throughout the entire study period. Treatment for prolonged seizures (>5 minutes) or clusters of seizures can be used per participant's previous rescue prescription.

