STUDY DESIGN	This is a prospective, single-center, phase 1 safety study to investigate the safety, tolerability, seizure control, and quality of life in participants with medically-refractory epilepsy who failed epilepsy surgery. These participants will have continued seizures despite being at least 3 months post-epilepsy surgery (resective surgery with an intent to cure). Upon enrollment, participants will be continued and observed on their pre-existing, clinically prescribed antiepileptic drug (AED) regimen for 1 month. At the 1-month mark, participants will receive weekly ABI-009 intravenously at different dose levels in cohorts of 3 participants each using the standard 3+3 dose-finding design. ABI-009 will be continued for a total of 3 weeks. ABI-009 will then be discontinued and the participants will be observed for an additional 3 months. We intend an expansion of the maximum tolerated dose (MTD) cohort to an estimated additional 6 participants for a maximum possible enrollment of 18 participants.
DURATION OF SUBJECT PARTICIPATION	Participants will be on study for about five months. Initial control period: 1 month Dosing period: 3 weeks

AND DURATION OF STUDY	Follow-up: 3 months
PRIMARY OBJECTIVE	
Safety and Tolerability:
 
 ▪ Determine dose-limiting toxicities (DLTs) and MTD of ABI-009 in participants with surgically-refractory epilepsy ▪ Record the adverse events (AEs) and document their severity with ABI-009 dosing for medically intractable epilepsy that has failed surgical resection, administered in conjunction with their pre-existing AED regimen. Record the compliance of families with medication and record the number of participants that withdraw from study either voluntarily or by necessity secondary to AEs. ▪ Columbia-Suicide Severity Rating Scale (C-SSRS) serious suicidal ideation score stays below a 4 rating.

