Dose-levels	ABI-009 in mg/m ²												
-2	1												
-1	2.5												
1	5												
2	10												
3	20												

	
then a new cohort of 3 participants at the next higher dose level can be enrolled. If 2/6 participants at dose level 1 experience a DLT, then that cohort will be closed to further enrollment and 3 participants will be enrolled at the next lower dose level, and so on. The MTD is the highest dose level in which ≤ 1 participant has a DLT.
 
Once the MTD has been determined, the MTD cohort will be opened for an additional 6 participants. These participants will adhere to the identical protocol of the rest of their cohort.
 
Product will be administered IV every seven days for three weeks.

CONTROL PRODUCT, DOSE AND ROUTE OF ADMINISTRATION	
There is no control product for this study. Participants will serve as their own controls by continuing their pre-existing AED regimen for 1 month after enrollment prior to starting dosing with ABI-009. In order to proceed with drug administration participants will have to have had >8 seizures in 30 days without 2 consecutive weeks of seizure freedom.

CONCOMITANT MEDICATIONS	
Allowed: Standard therapy for epilepsy is allowed except for treatments noted in the prohibited medications section below. Pre-existing AEDs must not be titrated while participants are enrolled in the study, unless the dose change is solely to address subtherapeutic levels as determined by the treating neurologist. Rescue medication is allowed for prolonged seizure event or cluster of seizures.
 
Prohibited: The following medication changes are prohibited during participation in the trial, and as such will be considered a protocol violation:
 
 • Any changes in dosage of AED regimen, unless solely to address subtherapeutic levels of AEDs as determined by the treating neurologist. • Any additions or removal of AEDs to the participant's AED regimen during participation unless medically necessary and discussed with investigator
PRIMARY ENDPOINT	
Safety:
 
DLT and MTD
 
Incidence of adverse events and clinically significant abnormal lab values
 
Tolerability:
 
Number of participants withdrawn from study
 
Adherence to prescribed ABI-009 regimen
 
Columbia-Suicide Severity Rating Scale (C-SSRS) serious suicidal ideation score stays below a 4 rating.

SECONDARY	
Efficacy:

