10 EVALUATIONS BY VISIT

10.1 Screening Assessments (Day -14 to 0)

1. Review the study with the participant (participant's legal representative) and obtain written informed consent and HIPAA authorization and assent, if appropriate.
2. Review eligibility (including epilepsy history)
3. Perform extended physical examination
4. Record demographics data
5. Record medical history, including a history of epilepsy, diagnosis date, and prior epilepsy treatments.
6. Vital signs (Height, pulse, blood pressure, respiration rate, temperature and weight)
7. Current medications and baseline conditions
8. Neurologic exam
9. Pulse oximetry (must be >93)
10. Laboratory assessments as required per the schedule of evaluations (need to be from within the last 30 days)
 - a. Complete Blood Count (CBC) with differential and platelet count
 - b. Blood chemistry assessment, including:
 - i. Sodium, potassium, chloride, bicarbonate, calcium, fasting glucose, albumin
 - ii. Total protein, BUN, serum creatinine
 - iii. Total bilirubin, AST, ALT, alkaline phosphatase, uric acid, phosphorus
 - iv. Fasting serum lipid profile (total cholesterol, triglycerides, HDL and LDL)
 - c. Coagulation assessment, including prothrombin time, partial thromboplastin time, international normalized ratio (PT/PTT/INR)

- d. Hepatitis B and C screening. Hepatitis B screening can be deferred in participants who have a history of having received the entire Hepatitis B immunization series and documentation is provided.
- e. Serum or urine pregnancy test: If participant is of child-bearing potential, pregnancy test should be done at screening and monthly thereafter. If urine test is positive, confirmatory blood testing will be performed.
- f. HIV seropositivity screening, if necessary.

11. If available and consent to archive has been given: Archival brain tissue tumor samples from a prior surgery will be used to test for molecular analyses. An email from the pathology/genetics department(s) may be used to confirm tissue availability at the time of enrollment.

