10.2 Visit 1 – may also be Screening visit (Day 0)

1. Review the study with the participant/participant's legal representative and obtain written informed consent and HIPAA authorization and assent, if appropriate.
2. Assign the participant a unique screening number.
3. Record concomitant medications.
4. Perform abbreviated physical exam
5. Measure and record height and weight.
6. Obtain and record vital signs.
7. Initiate epilepsy diary

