APPENDIX 1. SCHEDULE OF EVENTS

	SCREENING DAY -14 TO DAY 0*	VISIT 1: DAY 0	VISIT 2: DAY 30**	VISIT 3: DOSE 1	VISITS 4&5: DOSES 2 AND 3	VISIT 6: ONE WEEK POST- DOSING	VISITS 7&8: 30 AND 60 DAYS POST-DOSING	VISIT 9: 90 DAYS POST- DOSING	EARLY PERMANENT DISCONTINUATION
Informed Consent Process	X								
Enrollment Eligibility Checklist	X								
Demographics	X								
Extended Physical Exam	X								
Neurological Exam	X								
Hepatitis C, and Hepatitis B, HIV if necessary ^A	X								
Epilepsy and Medical History	X								
Height, Weight, and BSA	X			X				X	X
Vitals	X		X	X	X	X			
Pulse Oximetry ^F	X		X	X	X				
CBC with Differential ^C	X		X	X	X	X	X ^B (visit 7 only)		X
Serum Chemistries with Coagulation Assessment ^E	X		X	X	X ^B (visit 4 required)	X ^B	X ^B (visit 7 only)		X
Urine Pregnancy ^G	X		X						
Study Continuation Checklist			X	X	X	X	X		
Abbreviated Physical Exam		X	X	X	X	X	X ^D		X
Concomitant Medication Review		X	X	X	X	X	X	X	X
Dispense Seizure Diary and Glossary		X							
Administer QOLCE, NCBRF, & C-SSRS			X			X		X	X
Review Seizure Diary			X	X	X	X	X		X
Investigator Opinion			X	X	X	X	X		
Dosing Checklist				X	X				
Study Drug Administration				X	X				
Adverse Events			X	X	X	X	X	X	X
Whole Blood Rapamycin Level ^H					X	X			X

*Screening may be combined with Visit 1

**Visit 2 may also be Visit 3 Dose 1

^A Hepatitis C (and if necessary, Hepatitis B) test: 2 mL SST gold top tube. HIV seropositivity test, if necessary: 2 mL gold top tube. If testing for all together, can use one 4 mL SST gold top tube.

^B Only if previous chemistries or coagulation profiles are abnormal or are otherwise clinically indicated.

^C CBC with differential: 1 mL EDTA lavender top tubes if testing with blood trough rapamycin levels. If testing alone can collect only 0.5 mL in EDTA tube.

^D Only at 30 days post-treatment

^E 2 x 4 mL SST gold top tubes. Serum chemistry: Na, K, Cl, CO₂, Ca, fasting glucose, BUN, creatinine, total protein, albumin, total bilirubin, aspartate aminotransferase (AST/SGOT), alanine aminotransferase (ALT/SGPT), alkaline phosphatase, uric acid, Ph, fasting serum lipid profile. Coagulation assessment: 1.8 mL Sodium Citrate light blue top tubes. Coagulation assessment including prothrombin time, partial thromboplastin time, international normalized ratio (PT/PTT/INR).

^F Must be greater than 93% on room air to continue with study procedures

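### No entry criterion requires a stable AED regimen before baseline, so an AED effect still developing after Day 0 can bias the secondary seizure endpoints in either direction

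*Combined protocol and SAP*

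**What the plan says.** Section 7.1 on the time before and during baseline: "A stable therapeutic regimen between screening and Visit 1 is the goal, as well as through the baseline period". Once the baseline observation period has begun the rule is firm: "changes in AED medication regimen are not permitted unless it is solely for dose adjustments secondary to sub- or super-therapeutic serum levels".

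Section 10.1 places screening between Day -14 and Day 0. The Schedule of Events adds, in a footnote: "Screening may be combined with Visit 1". The heading of Section 10.2 says the same.

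None of the 13 inclusion criteria in Section 6.2 or the 12 exclusion criteria in Section 6.3 mentions time since the last AED change. Exclusion 9 sets a 30-day washout, for investigational drugs only. Exclusion 2 lets the investigator keep out anyone with a condition that would make the outcome data hard to interpret.

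The synopsis explains the comparison: "Participants will serve as their own controls by continuing their pre-existing AED regimen for 1 month after enrollment". Section 15.1 defines baseline as Days 0-30, Section 15.1.1 makes every analysis a within-participant pre/post comparison, and Section 15.5 counts a reduction of at least 25% as a response.

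**The concern.** The background AED regimen is the trial's only comparator for seizures. A pre/post contrast needs that comparator to be at steady state when baseline starts. The plan restricts AED changes from enrolment onward but sets no requirement on what happened just before.

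Suppose a candidate's AED was started or raised shortly before Visit 1. If its effect builds through Days 0-30 and beyond, the baseline rate is too high as a reference for the later periods, and the remaining fall is read as an ABI-009 effect. If an AED was reduced or stopped instead, the baseline is too low and a real ABI-009 effect is hidden. Improved seizure control is one of the two hypotheses in the synopsis, and no concurrent arm exists to separate the two causes.

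**Working it through.** The documents give no AED effect size, onset time or efficacy power, so there is no figure of the plan's to reproduce. The check asks how large the artefact could be.

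**Inputs from the documents.** Baseline is Days 0-30 (15.1). Dosing lasts 3 weeks, taken as Days 30-51. Follow-up runs to 90 days post-dosing (10.6), taken as Days 51-141. The responder cut-off is 25% (15.5). Both later windows are shown because the text compares baseline with follow-up in one sentence and with a maintenance phase in another.

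**Assumptions.** The AED change is made *s* days before Visit 1, its eventual proportional effect is *E*, its onset is exponential with half-time *h* days, and ABI-009 has no effect. These are expected rates and ignore random variation in counts.

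**Formulas.** With *t* the days since the AED change and k = ln2/h:

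- Rate: r(t) = 1 − E(1 − e^(−kt))
- Mean rate from t = a to t = b: 1 − E + E(e^(−ka) − e^(−kb)) / (k(b − a))
- Apparent reduction: 1 − (later mean / baseline mean), which is the protocol's percentage-reduction formula

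**Worked case: E = 50%, h = 14, s = 0.** k = 0.04951.

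- Baseline: 0.5 + 0.5 × (1 − 0.2264)/1.4853 = 0.7604
- Dosing: 0.5 + 0.5 × (0.2264 − 0.0801)/1.0397 = 0.5704
- Follow-up: 0.5 + 0.5 × (0.0801 − 0.0009)/4.4559 = 0.5089
- Apparent reduction in dosing: 1 − 0.5704/0.7604 = 25.0%
- Apparent reduction in follow-up: 1 − 0.5089/0.7604 = 33.1%

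**Range with the change on the day of Visit 1** (dosing / follow-up):

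| AED effect | h = 1 | h = 7 | h = 14 | h = 21 |
|---|---|---|---|---|
| 30% | 2.0% / 2.0% | 11.2% / 12.0% | 13.3% / 17.6% | 12.4% / 19.4% |
| 50% | 4.6% / 4.6% | 22.6% / 24.2% | 25.0% / 33.1% | 22.4% / 35.2% |
| 70% | 10.1% / 10.1% | 39.8% / 42.6% | 40.0% / 53.0% | 34.5% / 54.1% |

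Over half-times from 0.5 to 60 days, a 30% effect peaks at 13.3% in dosing and 19.6% in follow-up and never reaches the cut-off. A 40% effect peaks at 18.9% in dosing and passes 25% only in follow-up with slow onset (peak 27.1%). A 50% effect only just reaches it in dosing (peak 25.3%). A 70% effect is large enough to reach it at a half-time of 3 days (25.1% / 25.2%).

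**Opposite direction.** Replacing E by −E, a withdrawal that raises the rate by 30% with h = 14 gives an apparent worsening of 10.0% in dosing and 13.2% in follow-up.

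**Effect of a stable period** (E = 50%, h = 14; dosing / follow-up): none, 25.0% / 33.1%; 14 days, 15.1% / 20.0%; 28 days, 8.4% / 11.1%; 56 days, 2.3% / 3.0%.

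**Scale.** One wrongly classified participant moves the response rate by 1/18 = 5.6 percentage points at full enrolment.

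**The case against.** The best defence is the baseline itself. Every participant is observed for about 30 days on a restricted regimen before Dose 1, so even a change made the day before Visit 1 is about four weeks old by then. That stands for fast-acting changes: with a half-time of 1 day, a 50% effect leaves an artefact of only 4.6%. It does not cover effects still building after Day 0.

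Three further safeguards are partial. Exclusion 2 allows a recently adjusted candidate to be turned away but does not require it or mention AEDs. The requirement for more than 8 seizures in 30 days is applied again at Visit 2 and removes some strong responders to a new AED. In the worked case, though, anyone with about 12 or more seizures per 30 days before the change (9/0.7604 = 11.8) would still be expected to pass. AED history and medication dates are recorded, but no planned analysis uses them.

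A reader might infer more than the documents support:

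- **That any recent AED change produces a false responder, or that a 25% AED effect is enough.** A 25% effect does so only if it arrives wholly after Day 30. Under exponential onset it peaks at 10.8% in dosing and 16.0% in follow-up.
- **That such changes are frequent in this population.** The documents give no rate. The three months after surgery in inclusion 6 is a minimum interval and says nothing about AED changes.
- **That the bias always favours ABI-009.** A recent reduction or withdrawal works the other way.
- **That the dose-finding result is compromised.** DLT and MTD do not rest on seizure counts.

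**Conclusion.** The gap is real and modest. Stability before Visit 1 is an aim over 0 to 14 days, with no eligibility criterion behind it. The uncontrolled comparison with Days 0-30 cannot tell a developing AED effect from an ABI-009 effect. For AED effects of 30% to 50% and half-times of 1 to 21 days, the artefact in an affected participant is about 2-25% in dosing and 2-35% in follow-up. It reaches the 25% cut-off only near the large, slow end of that range. Effect size, onset shape and the number of participants affected are all assumptions or unknown. Only the secondary seizure endpoints are touched. The point merits a change because the remedy is cheap, not because the bias is shown to be large.

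**What to change.** 1. Replace the aim in Section 7.1 with a binding criterion in Section 6.2 and the synopsis: AEDs unchanged for a stated minimum period before Visit 1. Thirty days would match the existing seizure-count window; the sponsor sets the length. The calculation shows that a longer period leaves less residual bias but does not fix the number.
2. Record the date of the last AED change for each participant at screening.
3. In the SAP, which Section 15.1 says is still to be written, specify in advance a sensitivity analysis of the seizure endpoints that excludes participants with a recent AED change, with the cut-off for recent defined there.

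While editing Section 7.1, reconcile it with the synopsis: the former allows adjustments for levels that are too low or too high, the latter only for levels that are too low.

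The cost is amendment wording and one dated field; medications and epilepsy history are already collected at screening. A recently adjusted candidate would enter later, and Section 12.2 already allows rescreening up to three times.

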7.2 Prohibited Medications and Treatments

Administration of immunosuppressant or chemotherapeutic drugs, IV/PO corticosteroids prescribed outside the context of the investigational protocol, and attenuated live vaccines, as well as any investigational drugs or biologics, is prohibited while the participant is enrolled in the study.

8 STUDY DRUG DOSING

8.1 Method of Assigning Participants to Dosing Groups

Up to 18 eligible participants will be enrolled to receive the study drug (ABI-009). There will be no randomization, and this will be an open-label trial. Participants will be assigned according to a standard 3+3 dose escalation design, in the order that they are enrolled.

Participants must meet all inclusion criteria and no exclusion criteria should apply. The participant must have signed and dated an approved, current version of all applicable consent forms. To allow non-English speaking participants to participate in this study, bilingual health services will be provided in the appropriate language when feasible.

8.2 Blinding

This is an open label study; no blinding to dosing assignment will be performed.

8.3 Formulation of Test and Control Products

8.3.1 Formulation and Administration of Test Product

Refer to the Pharmacy Manual for complete information.

ABI-009 is provided as a lyophilized powder containing 100 mg rapamycin/vial. Each vial of study drug will be labeled per standard requirements.

8.3.2 Formulation of Control Product

No control product will be used in this study.

8.4 Supply of Study Drug to the Site

AADI will ship the study drug to the investigational site. The initial study drug shipment will be shipped after site approval to enroll (i.e., all required regulatory documentation has been received by AADI and a contract has been executed). Subsequent study drug shipments will be made as needed.

8.4.1 Dosage/Dosage Regimen

All participants receive study drug every 5-9 days for 3 weeks.

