1.10 Clinical Pharmacokinetics of ABI-009

Clinically, ABI-009 has unique characteristics amongst the available mTOR inhibitors. ABI-009 produced a fairly dose proportional increase of C_{max} and AUC across the dose range tested, and it significantly inhibited mTOR targets S6K and 4EBP1. The PK profile of rapamycin administered as ABI-009 is categorically different from those of the other oral or IV administered mTOR inhibitors. Intravenous infusion of ABI-009 from 45 to 150 mg/m² results in high C_{max} of rapamycin upon administration followed by a long half-life of approximately 60 hrs that allows once weekly dosing. Peak levels of rapamycin after ABI-009 are well above 1000 ng/mL range that may have significant tumor penetration effect. Oral mTOR inhibitors such as rapamycin or everolimus have poor absorption with a high inter- and intra-patient variability and a poor safety profile that requires low basal levels (low ng/mL level) to be maintained over the course of treatment. Temsirolimus on the other hand is a prodrug of sirolimus (rapamycin) and as a result, high levels of rapamycin are not achieved (< 100 ng/mL) [143]. Clinically, administration of ABI-009 at the maximum tolerated dose of 100 mg/m² IV weekly led to a much higher exposure to rapamycin (sirolimus) as compared with daily oral rapamycin at 5 mg/day (C_{max} 130-200 fold, AUC 16-27 fold, AUC/dose ~3-5 fold higher with ABI-009), temsirolimus weekly IV at 25 mg (C_{max} ~50 fold, AUC ~12 fold, AUC/dose ~2 fold for ABI-009), and daily oral everolimus at 4-10 mg/day (C_{max} 50-70 fold, AUC 12-29 fold, AUC/dose ~4-5 fold higher with ABI-009) [130, 143, 144]. Unlike with other mTOR inhibitors, micromolar concentrations are reached and maintained for several hours with ABI-009 which could potentially circumvent acquired resistance to mTOR inhibitors via retroactivation of AKT by TORC2 [145, 146].

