3.3 Exploratory Objectives

For children enrolled in the study who underwent epilepsy surgery at our institution, informed consent will be sought for us to use their previously acquired/banked surgical tissue (including fibroblast cultures) for the following exploratory aims:

- To explore associations between histopathologic diagnosis and seizure outcomes
- To explore associations between pS6 positivity and seizure outcomes
- To analyze key molecular features including activation of the PI3K, mTOR and MAPK pathways as they relate to seizure outcomes
- To possibly perform additional genomic studies or obtain previously performed genomic analyses including genomic profiling from peripheral samples and correlate to seizure outcomes
- Explore any relationships between safety, efficacy and whole blood rapamycin trough levels
- Explore any relationships between AED levels (acquired outside the study through clinical standard of care) and rapamycin levels during the study

None of the exploratory aims would require additional experimental procedures to the participants throughout the study beyond those explicitly discussed in the protocol. Tissue would only be tested on participants who have already consented to and have banked tissue within our institution from prior epilepsy-related procedures.

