4 STUDY DESIGN

4.1 Study Overview

This is a prospective, single-center, non-randomized open-label phase 1 study to investigate multiple dose levels of ABI-009 for surgically-refractory epilepsy. Up to 18 participants are planned to be enrolled into the study.

The duration of participation for each participant is up to 18 weeks, including a 4-week baseline period to obtain baseline outcome rates, a 3-week active study period and a 12-week follow-up period (see Figure 1). After the baseline period, participants will be started on the assigned dose of ABI-009, given once weekly for a total of 3 weeks. Dose levels to be tested are below:

For dose finding, ABI-009 will be tested in cohorts of 3 participants each using the standard 3+3 dose-finding design. Initial starting dose will be at 5 mg/m²/week.

Table 3: ABI-009 Cohort Dosing Schedule

Dose levels	ABI-009 in mg/m ²
-2	1
-1	2.5
1	5
2	10

3	20
---	----

Escalation to the next dose level with a new cohort of 3 participants will occur after no DLT was observed. There will be no intra-participant dose escalation allowed. If a DLT occurs in a cohort, an additional 3 participants will be recruited to the cohort. If no further DLTs occur, then a new cohort of 3 participants at the next higher dose level can be enrolled. If 2/6 participants at a dose level experience a DLT, then the cohort will be closed to further enrollment and 3 participants will be enrolled at the next lower dose level, and so on. The MTD is the highest dose level in which ≤ 1 participant has a DLT. There will be no intra-participant dose escalation allowed.

Once the MTD has been determined, the MTD cohort will be opened for an estimated additional 6 participants. These participants will adhere to the identical protocol of the rest of their cohort.

Product will be administered IV every 7 days for 3 weeks.

For a detailed review of visits, please see Appendix 1.

Total duration of the study is expected to be about one year.

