9.4 Research Laboratory Measurements

Whole blood rapamycin trough levels will be drawn for three consecutive weeks. If blood sample is unusable for testing, a second sample will be requested from the patient provided blood volume total is within safety range.

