10.4 Visits 3, 4, & 5: ABI-009 Doses 1-3 (+/-2 days)

1. Review adverse events.
2. Review epilepsy diary.
3. Investigator opinion regarding seizures recorded: same, worse, somewhat better, better.
4. Record changes to concomitant medications.
5. Perform abbreviated physical exam
6. Measure and record height and weight.
 - a. BSA calculation (Calculated ONLY on Dose 1 visit; to be recalculated only if the weight changes by > 10% in subsequent cycles)
7. Obtain and record vital signs. Pulse oximetry must be >93 to continue.
8. Collect blood for clinical laboratory tests (chemistry, hematology).
9. Laboratory assessments as required per the schedule of evaluations
 - a. Complete Blood Count (CBC) with differential and platelet count
 - b. Blood chemistry assessment (required for Visit 4), including:
 - i. Sodium, potassium, chloride, bicarbonate, calcium, fasting glucose, albumin,
 - ii. Total protein, BUN, serum creatinine.
 - iii. Total bilirubin, AST, ALT, alkaline phosphatase, uric acid, phosphorus,
 - iv. Fasting serum lipid profile (total cholesterol, triglycerides, HDL and LDL)
10. Coagulation assessment, including prothrombin time, partial thromboplastin time, international normalized ratio (PT/PTT/INR)
11. Whole blood rapamycin trough levels
12. Dose modification as appropriate (only in the case of toxicities mandating a dose change as per section 8.6)
13. Administer study drug

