12 DISCONTINUATION AND REPLACEMENT OF PARTICIPANTS

12.1 Early Permanent Discontinuation of ABI-009 Dosing

A participant may be permanently discontinued from ABI-009 dosing at any time if the participant, the investigator, or the Sponsor feels that it is not in the participant's best interest to continue. The following is a list of possible reasons for early permanent discontinuation of study treatment:

- Participant or participant's legal representative decision
- Protocol violation
- C-SSRS serious suicidal ideation score is increased to a 4 rating
- Death
- Pregnancy
- Refusal to complete patient diary, QOLCE, NCBRF, or C-SSRS questionnaires

If a participant is permanently discontinued from dosing early due to an adverse event, the participant will be followed and treated by the Investigator until the abnormal parameter or symptom has resolved or stabilized.

All participants who permanently discontinue study dosing early should come in for an early permanent discontinuation of study treatment visit as soon as possible and complete all remaining scheduled visits and procedures.

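### Rapamycin troughs may be drawn 5 to 9 days after a dose with no planned allowance for elapsed time, which would mainly weaken the level-response and level-safety analyses

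*Combined protocol and SAP*

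**What the plan says.** - **Dosing interval.** Section 8.4.1: "All participants receive study drug every 5-9 days for 3 weeks". Section 4.1: "Product will be administered IV every 7 days for 3 weeks". The synopsis agrees with 4.1. Section 8.6.3 adds only an intention to keep closely to the weekly schedule.
- **Sampling.** Section 9.4: "Whole blood rapamycin trough levels will be drawn for three consecutive weeks". At the dosing visits (10.4, window of 2 days either way) the level is listed ahead of drug administration, so it falls at the end of the preceding interval. Visit 6 (10.5) takes a level one week after dosing, with the same window. Section 9.3 rules out other pharmacokinetic measurements.
- **Which visits.** Section 10.4 lists "Whole blood rapamycin trough levels" for Visits 3, 4 and 5, although Visit 3 precedes any drug. Appendix 1 starts the level at Visits 4 and 5, continues at Visit 6, and adds one at early permanent discontinuation. The list for that last visit in 10.7 has no rapamycin level. Section 12.1 says such participants "should come in for an early permanent discontinuation of study treatment visit as soon as possible".
- **Use.** The blood level-response relationship is a secondary endpoint (5.2, 15.5). Section 3.3 adds the exploratory aim: "Explore any relationships between safety, efficacy and whole blood rapamycin trough levels". Section 15.5 gives the t-test and ANOVA as examples of method. I found no sampling window in hours, no instruction to record draw time against infusion time, and no adjustment for elapsed time. Section 15.1 leaves detail to a SAP still to be written.
- **Kinetics.** Section 1.10 describes a high peak in adults, "followed by a long half-life of approximately 60 hrs that allows once weekly dosing". Table 1 in 1.13 predicts levels by hour, and the same section says no pediatric PK data exist.

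**The concern.** Trough levels can be compared between participants only if they are taken at the same time after the dose, or if the time is allowed for. The permitted spread of 96 h covers 96/74.3 = 1.3 to 96/60 = 1.6 half-lives, so timing alone moves the level appreciably. Timing variation of that kind in an explanatory variable pulls its slope towards zero. With at most 18 participants and no other exposure measure, there is little information to lose.

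A second, conditional problem concerns toxicity. If a participant's dose is held and the sample is taken only at the delayed dosing visit, the level is low because of the delay. Holds are triggered by toxicity, so that error would not be random with respect to safety.

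Draw times that were never captured cannot be restored reliably, so a later SAP may be too late to solve this alone.

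**Working it through.** **1. Reproduce the plan's half-life.** Inputs are the 5 mg/m² row of Table 1: 18.18 ng/mL at 24 h, 12.15 at 48 h, 6.97 at 96 h, 3.56 at 168 h. Formula: half-life = Δt × ln 2 / ln(C1/C2).
- 24 to 168 h: 144 × 0.693 / ln(18.18/3.56) = 61.2 h. A log-linear least-squares fit over the same span gives 64.1 h. Both agree with the stated figure of about 60 h.
- 96 to 168 h: 72 × 0.693 / ln(6.97/3.56) = 74.3 h.

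I use 60 to 74.3 h as the range. Table 1 is dose-proportional to within 0.3%, so the ratios below apply at every dose.

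**2. Level by draw day.** Level(t) = C168 × 2^(−(t − 168)/half-life), with C168 = 3.56, 7.11 and 14.22 ng/mL at 5, 10 and 20 mg/m². This assumes mono-exponential decline after a single dose. Values past 168 h are extrapolated.

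| Dose and draw day | Half-life 74.3 h | Half-life 60 h |
|---|---|---|
| 5 mg/m², day 5 | 5.57 | 6.20 |
| 5 mg/m², day 7 | 3.56 | 3.56 |
| 5 mg/m², day 9 | 2.27 | 2.04 |
| 10 mg/m², day 9 | 4.54 | 4.08 |

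**3. Compare with the dose steps.**
- Two days off day 7: 2^(48/74.3) = 1.57; 2^(48/60) = 1.74.
- Day 5 against day 9: 2^(96/74.3) = 2.45; 2^(96/60) = 3.03.
- Escalation steps: 10/5 = 20/10 = 2.0. The lowest step is 2.5/1 = 2.5, which 2.45 just misses and 3.03 exceeds.

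At the extremes, 5 mg/m² on day 5 (5.57 to 6.20) reads above 10 mg/m² on day 9 (4.08 to 4.54).

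**4. Illustrate the attenuation.** Assumptions: draw day uniform on 5 to 9 and unrelated to outcome; between-participant SD of log level = ln(9.1/4.3)/1.693 = 0.443. That SD treats the range in 1.13 for adults at 5 mg/m² as three values, and 1.693 is the expected range of three standard normal values.
- Timing SD = ln 2 × 96/(half-life × √12) = 0.259 at 74.3 h, 0.320 at 60 h.
- Slope retained at one dose: 0.443²/(0.443² + 0.259²) = 0.75; 0.443²/(0.443² + 0.320²) = 0.66.

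Timing is then 25% to 34% of the variance in log level at a fixed dose, and a smaller share across dose levels.

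**5. Conditional cases.**
- If a hold moves the draw from day 7 to day 14, the level is 2^(−168/74.3) = 0.21 or 2^(−168/60) = 0.14 of the day-7 value.
- If a discontinuation sample happened to fall at 24 or 48 h, Table 1 gives 18.18/3.56 = 5.1 or 12.15/3.56 = 3.4 times the 168 h level.

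**6. Effect of normalising to 168 h.** A day-5 level is multiplied by 1/1.74 to 1/1.57 (0.57 to 0.64), and a day-9 level by 1.57 to 1.74. Using the wrong end of the 60 to 74.3 h range leaves 3.03/2.45 = 1.24-fold between the window ends, instead of 2.45- to 3.03-fold.

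**The case against.** The case for leaving the plan alone has real force.

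- **The dose-step contrast is a worst case.** It needs one sample at each end of the window. A single 2-day deviation stays below a 2-fold step, and the stated intention is weekly dosing. A uniform spread of draw days is pessimistic. This stands.
- **A reader might infer that the level reflects timing as much as exposure.** The figures do not support that: even under the uniform assumption, timing is about a quarter to a third of the variance at a fixed dose.
- **A reader might infer that toxicity holds push levels down in exactly the participants with toxicity, masking or reversing a true relationship.** The text does not say that the draw moves with the dose. In 10.4 the level precedes the dose-modification step, so toxicity found at a scheduled visit can have an on-time sample, and 9.4 ties draws to consecutive weeks. Table 4 also lowers the dose in several cases, so a later low level may be genuine.
- **A reader might infer that early-discontinuation samples contaminate the troughs.** Appendix 1 calls that row simply a blood level, and no section pools it with the weekly troughs.
- **The gap may be filled elsewhere.** The SAP is still to come, and the CRF is not among the documents, so times may already be captured.
- **Correction has limits.** The slopes are adult figures, and 8.6.1 allows CYP3A4 inducers without ABI-009 adjustment. The 74 h segment starts from a 96 h value barely below the 72 h one (6.97 against 7.10). Five-day spacing is also genuinely more intensive dosing, so normalising removes some real exposure difference.

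What remains is that the window is written into the plan, its effect is not small, and no stated analysis allows for it.

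**Conclusion.** The concern holds, at moderate weight. A compliant trough can lie anywhere from 120 to 216 h after a dose. On the protocol's own kinetics this means 1.57- to 1.74-fold for a 2-day deviation and 2.45- to 3.03-fold between the window ends, against 2-fold escalation steps. The expected consequence of using unadjusted levels is mainly attenuation. Under the illustrative assumptions, a slope at one dose keeps about 66% to 75% of its size. The actual loss cannot be computed because the draw times are unknown.

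A differential error in level-safety is possible only if draws follow held doses, which the plan should settle. A claim of established bias or reversal goes beyond the documents. Dose escalation and the MTD do not use the levels, so the primary objective is untouched.

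These results rest on adult PK predictions, mono-exponential decline after 96 h, and extrapolation beyond 168 h.

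**What to change.** 1. Record infusion end time and blood draw time on the CRF, if it does not already do so.
2. In 15.5 and the SAP, define the exposure variable from the Visit 4, 5 and 6 levels. Either include actual elapsed hours and the dose given in the level model, or normalise each level to 168 h. Modelling is the better choice where differences in dosing interval should not be removed.
3. Repeat the analysis over a range of half-lives that includes 60 to 74 h and extends beyond it, to allow for the lack of pediatric data and for CYP3A4 inducers.
4. State whether the draw moves when a dose is held. Keep post-hold samples in the main analysis with their actual elapsed time, and show results without them only as a sensitivity analysis. Dropping them outright would select on toxicity.
5. List early-discontinuation levels separately from the weekly troughs.
6. Reconcile 10.4 (Visit 3) and 10.7 with Appendix 1, and the 7-day statements with the 5-9-day statement in 8.4.1.

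The cost is two time fields and some SAP wording, with no extra blood draws. The downside is reliance on an assumed terminal slope taken from adult data, which the wider sensitivity range shows but does not remove.
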